### 12-month outcomes

We will examine the same outcomes at 12 months as we did at 6 months. In doing so, we will be comparing the treatment group (which will have had 12 months of exposure to the FFF program) to the control group (which will have had 6 months exposure to the FFF program). This will be informative about whether the rate of expected improvement in outcomes slows over time.

Health care utilization will also be examined at 12 months. As mentioned earlier, we expect that any effect of FFF on utilization may be visible only with a lag. We have statistical power for the more common 12-month outcomes: any inpatient stay, any ED visit, and any hospital visit (inpatient or ED). We will also examine the number of such visits, as well as the number of outpatient visits outside the Fresh Food Farmacy.

To allow time for the program to affect outcomes, we will also consider outcomes within other timeframes: 90-365 days and 90-180 days.

The program re-assesses food insecurity after one year, so food insecurity will be asked at 12 months; given the nature of the program we hypothesize that the FFF program should considerably reduce food insecurity.

## Diet and Healthy behaviors

The 6- and 12-month surveys also ask about diet, exercise, and smoking behavior. In addition, whether routine examinations such as eye exams have been conducted are asked in the survey—measures that we can verify in the electronic health record for exams conducted at Geisinger. This will provide some information about utilization outside of Geisinger and serve as a check on the accuracy of the survey responses.

To investigate whether the Fresh Food Farmacy is a complement to other healthy behaviors, we will investigate changes in behaviors that we can observe in addition to the survey questions. These include the rate at which the subjects make other appointments at Geisinger. We also plan to investigate medication adherence. As a separate, related outcome, we will look at drug utilization for drugs used to treat diabetes to test whether the Fresh Food Farmacy can substitute for this treatment.

In addition, the EHR data will allow us to determine whether a subject completes wellness visits in terms of PCP and endocrinologist visits along with diabetes Healthcare Effectiveness Data and Information Set (HEDIS) measures, as another set of healthy behaviors that may be improved as a result of program participation.

### Other Household members

Recall that FFF provides fresh food for all members of the participant's household. We will test whether the FFF program has spillover benefits to these other household members. Using address information, we will examine such household members that appear in the Geisinger EHR data and test for impacts on lab results and healthcare utilization.

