8.2 Study Population

8.2.1 Approximate Number of Subjects

[figure not shown]
Approximately 500 Geisinger subjects will participate in this study with about half assigned to the treatment group and about half to the control group. Approximately 2000 household members will be included in the data-only portion of the research.

There are 3 groups of subjects identified in this prospective protocol.

Group 1- Will be randomized to the treatment ("Begin Now") group for the FFF program. Subjects will be consented to join the FFF study prior to learning their program start date. They will join the FFF program right away when the program opens in their geographic area. Data will be collected during the first 12 months of subject participation and EHR and claims data may be analyzed for an additional 12 month follow-up period (24 months in total).

Group 2- Will be randomized to the control ("Begin Later") group for the FFF program. These subjects will be consented to join the FFF study prior to learning their program start date. They will join the FFF program approximately 6 months after the program opens in their geographic area. Data will be collected during the first 6 months of subject participation and used as control data for the study. EHR and claims data may be analyzed for an additional 12 month follow-up period (24 months in total from the start of the trial).

Group 3- Household Member data. Consented subjects will be asked for the names and dates of birth (DOB) of individuals living in their household who will be consuming food and benefiting from the FFF program. A waiver of consent is being requested in order to access health

information from the household members' medical records. EHR and claims data may be analyzed 24 months from the start of the trial by a household member.

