The FFF program provides food for the entire household. As a result, we are requesting data on household members as well. For the prospective study, household members are identified by the subject to ensure an accurate listing of household members who are actively benefiting from the program. Pulling data using the same address may lead to including household members who are not actively living in the residence (e.g. college student who is not living at home). FFF plans to ask members about their family members in the future, and this will be used to check the household record extraction as well. Data will be provided to MIT with an encrypted household identifier. While we will not have follow-up visits with family members, we aim to observe clinical measures as they appear in the electronic health record. Household IDs will facilitate this analysis.

The retrospective data analysis will include the same data as the prospective study; however, household members will be identified by a shared home address due to no patient contact.

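### The SAP finds trial participants' household members by address, but the protocol has the subject name them; the secondary spillover sample therefore has two different definitions

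*SAP*

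**What the plan says.** The SAP covers only the randomised trial. Its household paragraph in section 3.3 reads: "Using address information, we will examine such household members that appear in the Geisinger EHR data and test for impacts on lab results". It also covers healthcare utilisation, and it mentions no list supplied by the participant.

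The protocol sets the rule for the prospective study in three places:

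- Section 8.2.1, Group 3: "Consented subjects will be asked for the names and dates of birth (DOB) of individuals living in their household", limited to those who will eat the food. The planned number is given there: "Approximately 2000 household members will be included in the data-only portion of the research".
- Section 9.2.1: "For the prospective study, household members are identified by the subject to ensure an accurate listing of household members". The reason follows: "Pulling data using the same address may lead to including household members who are not actively living in the residence".
- Section 12.1 repeats the rule and the reason when it requests the waiver of consent and HIPAA authorisation for household members.

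For the retrospective analysis, section 9.2.1 gives the other rule: "household members will be identified by a shared home address due to no patient contact". Section 7.2.1 likewise defines retrospective household members by residential address.

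On the model, Protocol 9.1.1 writes an intent-to-treat OLS regression for both specific aims, and Aim 2 (section 5.3) includes family members. SAP section 4 writes the same regression for subject i, with that subject's own randomised arm, strata and lagged outcome. Neither document says how the model carries over to household members. Section 9.2.1 does supply an encrypted household identifier.

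**The concern.** The SAP states for the trial the rule that the protocol assigns to the retrospective study, where nobody can be asked. An extraction built from the SAP and one built from the protocol would give different samples for the same secondary analysis. Three things are at stake.

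1. Dilution. An address match may include people who do not share the food. They carry little or no effect, so they pull the spillover estimate toward zero.
2. Coverage of the waiver. Section 12.1 describes the members as identified by the subject. A person found only by address does not fit that description.
3. Pre-specification. SAP section 1 says the plan is there to record the analyses in advance. Two possible samples leave a choice open.

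A smaller gap sits in the same place. Household members are not randomised; they share the index participant's arm. The plan does not say so, and does not say how correlation within a household is handled.

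**Working it through.** **Step 1: the two rules side by side**

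| | Prospective trial | Retrospective study |
|---|---|---|
| Protocol 8.2.1, 9.2.1, 12.1 | named by the subject | – |
| Protocol 7.2.1, 9.2.1 | – | shared address |
| SAP 3.3 | address, matched to the EHR | not covered |

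The entries for the prospective trial differ. The protocol gives its reason for not using address there, so the difference is one of substance.

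**Step 2: dilution**

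Neither document gives a sample size, power or target effect for household members, so there is no planned figure to reproduce. Let f be the share of address matches who do not share the food. Assume no effect in them and the same f in both arms. Then

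expected estimate = (1 − f) × effect in exposed members,

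and the sample needed for the same power is multiplied by 1/(1 − f)².

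| f (assumed) | Effect retained | Sample multiplier |
|---|---|---|
| 0.05 | 95% | 1.11 |
| 0.10 | 90% | 1.23 |
| 0.20 | 80% | 1.56 |

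**Step 3: clustering, as a bound only**

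This step applies only if members were analysed as independent, which the documents do not say. Inputs: about 2000 members and about 500 subjects (Protocol 8.2.1), so at most 2000/500 = 4 members per subject on average. The intraclass correlation (ICC) is assumed.

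Design effect DE = 1 + (m − 1) × ICC; the interval should be √DE times as wide; actual two-sided error of a nominal 5% test = 2 × [1 − Φ(1.96/√DE)].

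| Members analysed per household | ICC 0.05 | ICC 0.10 | ICC 0.30 |
|---|---|---|---|
| 1 | 5.0% | 5.0% | 5.0% |
| 2 (DE 1.05 / 1.10 / 1.30) | 5.6% | 6.2% | 8.6% |
| 4 (DE 1.15 / 1.30 / 1.90) | 6.8% | 8.6% | 15.5% |

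The last row needs every planned member to have an outcome. The protocol plans no follow-up visits for family members and says only that "we aim to observe clinical measures as they appear in the electronic health record". If each of 4 members independently had an outcome with an assumed chance s = 0.25, DE = 1 + 3 × s × ICC = 1.0375, 1.075 or 1.225, and the error would be 5.4%, 5.9% or 7.7%.

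**Step 4: timing of the named list**

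SAP section 2 describes one telephone call: the programme is described, consent is sought, and the patient is then randomised. Protocol 8.2.1 says consented subjects are asked for the names, but neither document says whether this is before or after the arm is revealed. If it is after, a subject about to receive food for the household and one told to wait six months might name different numbers of people. The named list would then be selected after randomisation, with bias of unknown direction.

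**The case against.** Four arguments count against the point.

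- **The SAP wording may be old.** The SAP speaks of an April 2019 launch as still to come, while the protocol carries an IRB approval date of 24 February 2020. The protocol text is explicit and under IRB control.
- **Address may be only a linking step.** The SAP paragraph starts from the household members who receive food, so address could simply help find them in the EHR. Section 9.2.1 also plans to ask about family members in future and says "this will be used to check the household record extraction as well".
- **The analysts will not hold addresses.** Protocol 12.2 strips address from the data set before it goes to MIT, so an address match could be made only at Geisinger, against the protocol's own rule.
- **Address has one advantage.** An address on file before enrolment cannot depend on the arm; a list taken after assignment can.

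The first three make a literal reading of the SAP less likely to be acted on. They do not remove the conflict: the SAP mentions no named list, and the extraction at Geisinger could still follow it. The fourth stands and shapes the remedy.

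A reader might also infer that no model exists for household members and that their tests will run at up to 15.5%. The documents do not support this. Protocol 9.1.1 writes the OLS model for both aims, and Aim 2 includes family members. No standard-error method is stated for any analysis, so silence here is not a decision to ignore clustering, and a household identifier is supplied. The 15.5% also needs an outcome for all four members and an ICC of 0.30.

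**Conclusion.** The conflict over who counts as a household member is real and should be resolved. The size of the dilution rests on an undocumented share of unexposed address matches, so the range in Step 2 illustrates it and is not an estimate. It also assumes no effect in unexposed people. Only the secondary spillover analysis is affected.

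On the waiver, the documents support a limited statement: members found only by address would fall outside the group that section 12.1 describes. A reader might infer that such people have been included without authority, but nothing shows that an address extraction for the trial was made.

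The missing statement on inherited arm, strata and standard errors is a minor clarification. Any inflation depends on an assumed ICC and on an undocumented number of members with EHR outcomes per household; with one member per household there is none.

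**What to change.** 1. **Definition.** Reword the SAP's household paragraph so that the sample is the subject-named list linked to the EHR, with address used only to locate or check named people. Do not add an address-matched analysis set unless the approved waiver covers it.
2. **Timing.** Where still possible, fix the list after consent and before the arm is revealed. Otherwise report the number of members named per subject by arm, so that any difference in naming can be seen.
3. **Model.** State that the OLS intent-to-treat model, applied to household members, uses the index participant's randomised arm and strata, with standard errors clustered on the household identifier.

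Items 1 and 3 cost a few sentences in a dated later version of the SAP, which its section 1 allows. They need no new data, since the list and the identifier are already in the protocol. At the ICCs assumed above, clustered intervals would be no wider with one member per household, about 2% to 14% wider with two, and about 7% to 38% wider with four. Fixing the list earlier under item 2 may need a change to the recruitment script (Protocol 8.2.4) and IRB approval before use (12.3), and it helps only subjects not yet recruited. Reporting the counts by arm needs only the list itself.

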# 4. Empirical Model

Our initial analysis will estimate intent-to-treat models using linear regression. Consider an outcome,  $Y_i$ , such as HbA1c, for each subject i. The primary specification is:

$$Y_i = \beta_0 + \beta_1 1(\text{Treatment})_i + \beta_2 X_i + \varepsilon_i$$

For our analysis,  $1(\text{Treatment})_i$  is an indicator equal to one if the subject was randomized to the treatment group and zero if the subject was randomized to the control group;  $X_i$  is a vector of control variables. These control variables should be uncorrelated with the treatment indicator, but they can aid in the precision of the estimate because they are correlated with the outcome Y. First, we will include strata indicators for location and HbA1c category. We will also include the lag of the dependent variable, which substantially improves power: for clinical test results that would be the most recent test result prior to enrollment in the study. For utilization outcomes such as inpatient visits, we will include the number of such episodes observed in the 12 months prior to study enrollment.

We also plan to include standard demographic controls: age (5-year age bins), sex (indicator that the patient is male), race/ethnicity (indicators for African American and Hispanic). For the clinical test results, we will also include a control for the number of days from the baseline measure to the follow-up test in order to improve precision. If this number of days is not balanced across treatment and control, we will control for the number of days between the baseline test and the date of enrollment into the study. We will also include the month-year of entry into the study unless this measure is highly correlated with the number of days between blood tests and reduces statistical precision.

We will also estimate models where the outcome is the difference between the baseline and the follow-up exam instead of including the baseline exam result as a control:

$$\Delta Y_i = \beta_0 + \beta_1 1 (\text{Treatment})_i + \beta_2 X_i + \varepsilon_i$$

This is a more restrictive model but may improve statistical precision and requires fewer controls. For models that control for lagged values or in this difference model, we will estimate models for those with non-missing values. We will also test whether missing lagged value is balanced across treatment and control for each measure. Note that all patients have a baseline HbA1c that was used in recruitment.

To consider robustness, we will report models with only strata indicators as controls, strata indicators plus the lag of the dependent variable because this substantially improves statistical power, and models with full controls.

The coefficient  $\beta_1$  measures the effect of intention-to-treat: the causal effect of being randomized into the treatment group. This can differ from the effect of the program if there is non-compliance: some subjects randomized to the treatment group may decide not to join the FFF program or may quit it after a short time. (Given the value of the free food, we expect that refusal and dropout rates will be low.) At the initial pilot site of Shamokin PA, 17% of those who began the program were no longer in the program at 6 months.

As an alternative specification, we will estimate the equation using Two Stage Least Squares (2SLS), with the initial randomized assignment to treatment or control used as an instrumental variable for the fraction of months engaged in FFF. The 2SLS estimate measures the average causal effect of the program for those who choose to remain in it as a complementary parameter to the intent-to-treat analysis described above.

That is, for subject i the structural equation is:

HbA1c at 6 monthsi = 
$$\beta_0 + \beta_1 \left\{ \left( \frac{1}{6} \right) * \text{Months of Engagement} \right\}_i + \beta_2 X_i + \varepsilon_i$$

And the first-stage is:

Months of Engagementi = 
$$\alpha_0 + \alpha_1 Treatment_i + \alpha_2 X_i + \vartheta_i$$

We re-scale the months of engagement in the structural equation by 6 for 6-month outcomes, and by 12 for 12 month outcomes so that the interpretation of our estimate of  $\beta_1$  is for full engagement, which eases comparisons to the intent-to-treat estimates.

In addition, if there is differential attrition from the study across treatment and control groups (despite our efforts to obtain outcomes from each subject including obtaining multiple forms of contact information for subjects and their family members and compensation for subjects' time)

we will explore bounding estimates under a range of assumptions about effect sizes for those not observed.

For survey responses that include categorical answers, outcomes will be binary measures of whether the answers are in the top and bottom quintiles as separate outcomes and will test robustness to using nonlinear estimators such as the multinomial logit. To avoid concerns about multiple hypothesis testing for multiple measures within each category of questions (diet, other healthy behaviors, diet understanding, diabetes understanding, self-assessed health, self-efficacy, and patient satisfaction), we will compile answers to these questions into indexes and test effects of the program on a change in these indexes. We will also report p-values corrected for the multiple tests when presenting results for each question individually.

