9.2 Data Management

9.2.1 Data Collection and Storage

Only approved study staff will have access to data collected for this research.

Administrative data are collected by Geisinger's data broker. For the prospective RCT, under a Data Use Agreement reviewed by the Privacy Office/ISO, a limited dataset stripped of personal identifiers will be transferred securely to MIT.

For the retrospective data exploration, PHI will be de-identified in accordance with a limited data set as allowed by the Research Collaboration Agreement between Geisinger and MIT. The historical data includes diabetic subjects and their household members from Northumberland,

Mifflin, Juniata, and Lackawanna counties where our goal is to compare program participants to non-participants as described above.

Once the data set is sent to MIT, the research team will review it for analysis. The resulting analytic file will be stored in a password-protected database on MIT's secure network. Only research team members can access the data files. The research team members will review the charts and gather all the needed information.

[figure not shown]
The limited dataset for the prospective portion of the study will also include dates of service and ZIP codes.

It will also include information relevant to all encounters:

- Admissions/discharges, clinical procedures, medications administered, problem list entries, and lab values
- Baseline demographic variables of patients (age, sex, ethnicity, payer, comorbidities)
- FFF Program participation

Paid claims summed over various categories of care and timeframes around program entry are requested from Geisinger Health Plan as well.

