Recruitment will be conducted over the phone; the program will be described, consent will be sought, and then patients will be randomized to either treatment ("start FFF now") or control ("start FFF later"). Note that all patients eligible for FFF, whether or not they agree to participate in the study, will be randomized to determine the timing with which they will enroll in FFF. This is the way the program is being introduced, akin to a lottery, and ensures that there is no incentive to refuse to participate in the study in order to start FFF sooner. Recruitment staff will discover whether the patient is randomized to start now or start later in a tamper proof REDCap application, which consults a randomized allocation table that the recruiter cannot access and a treatment status that is locked along with the patient's identifying information and study ID. The recruiter will then set up the patient's first appointment for those in the treatment group and will reach out to patients 5 months later to set up appointments for the group randomized to start later. We anticipate finding the patients 5 months later because all subjects are Geisinger Health patients, whose current address is on file, and we will ask for two other contacts at the time of recruitment.

The randomization is stratified using levels of HbA1c: <8.0 (in the event that the threshold is lowered),  $\geq$ 8.0 and <9.5, and  $\geq$  9.5 to attempt to ensure balance on a key pre-study control and because we are interested in estimating effects separately by these categories to inform

threshold setting in future applications. The randomization happens separately by location (Scranton and Lewistown) as well.

The trial will launch in April 2019 in Scranton, and likely June 2019 in Lewistown. We plan to continue enrollment until we attain at least 500 subjects (half in treatment) or when the recruitment period has lasted 2 years. If recruitment slows, we will consider lowering the eligibility threshold to an HbA1c of at least 7.5 rather than 8.0, and we may consider expanding the geographic limit.

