### Planned Heterogeneity Analysis

In addition to outcome comparisons across all of the participants, we will consider heterogeneous treatment effects across patients. First, a priori we are interested in whether the program is especially effective for different levels of baseline HbA1c in order to help target the program in the future. For example, if effect sizes decrease with the baseline A1c, we may want to expand the program to those with A1c  $\geq$  7.5.

We are also interested in whether the program has different effects across the two locations (Scranton and Lewistown) to investigate the external validity of the estimates.

We will also test for different effects of the program by sex, as the cooking instruction may differ in effectiveness for men versus women. Household structure may be important given that the food goes to the household: differences between single and multi-person households will be estimated.

We hypothesize that the FFF program may have greater impacts among those of lower income (for whom the food may be especially helpful) and may vary across education levels (those with more education may be better able to utilize the information they are given about food preparation and diabetes management or they may already possess that information); these hypotheses will be tested using ZIP code level education and income measures, although there

may be little variation. We will also test differences by type of payer, with Medicaid providing another proxy for income as well as independent interest in effects for this group given interest among Medicaid systems in this type of intervention.

To further investigate the importance of information, we can compare results for individuals who score relatively well on the baseline survey questions about understanding of diabetes and diet. We will create a score for those questions and split the sample based on the median value of the initial knowledge. Another source of heterogeneity that could be considered in other contexts is the cost of using the program. We plan to compare results by distance between home and the clinic based on the median distance to the clinic from the residential ZIP code.

HbA1c can be affected by diet, lifestyle, and drug adherence. To consider the latter, we will compare patients who are on insulin versus those who are not on insulin at the start of the trial.

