## Statistical Power and Sample Size Considerations

Using data for current (i.e. self-selected, non-randomized) FFF participants, we conducted parametric power calculations. These take into account the increase in power from controlling for baseline characteristics, but qualitatively similar results were found when we did not include

controls and when we used nonparametric (simulation) methods to estimate power. Similar results were also found when we based the calculations on similar patients in the counties where the two new sites (Lewistown and Scranton) will be located. All power calculations were conducted using STATA Version 15.

The table below shows that with the expected sample size of 500 we will have substantial power to detect small minimal detectable effects (MDE), as well as the ability to conduct heterogeneity analyses for the clinical outcomes. For utilization outcomes, we will have power to detect the (albeit) large reductions in utilization found in the observational literature.

Table 2: Statistical Power to Detect Targeted Minimal Detectable Effects (MDE)

					Required N for
	Mean	Std.Dev.	$\sqrt{1-R^2}$	Target MDE	MDE
Variable					
HbA1c after 180 days	8.58	1.74	0.66	10%	55
HbA1c after 365 days	8.56	1.67	0.66	10%	56
Weight after 180 days	228	64	0.96	10%	228
Weight after 365 days	228	64	0.96	10%	228
Hospital Visit (Inpatient or ED) 0-180 days	0.39	0.49	0.85	30%	397
Hospital Visit (Inpatient or ED) 0-365 days	0.48	0.50	0.87	30%	278
Hospital Visit (Inpatient or ED) 90-365 days	0.40	0.49	0.92	30%	447

We subsequently simulated statistical power for a model that estimates the effects of full engagement. For our primary outcome of HbA1c at 6 months, with power=80% and alpha=0.05 and planned sample size of 500, we can detect:

• Intent to treat effect of assignment to treatment: reduction of 3.7%

• IV treatment effect of full engagement: reduction of 5.2%

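### The utilization models leave out baseline comorbidity, payer and other prior visit types that the trial already extracts; a short prespecified addition could sharpen the secondary outcomes with the least sample-size margin.

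*SAP*

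**What the plan says.** SAP section 4 (Empirical Model) gives one regression for all outcomes. For hospital use, its controls are the randomization strata (site and HbA1c band), age in five-year bins, sex, race/ethnicity, month-year of entry under a condition, and a lag term: "For utilization outcomes such as inpatient visits, we will include the number of such episodes observed in the 12 months prior to study enrollment". Protocol 9.1.1 speaks of prior-utilization controls only in general terms.

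The data are wider than that list. Protocol 9.2.1 includes "Baseline demographic variables of patients (age, sex, ethnicity, payer, comorbidities" in the extract, and SAP 3.1 says that the health record holds inpatient, outpatient and ED encounters. Comorbidity is not mentioned in the SAP. Payer enters only as a subgroup: "We will also test differences by type of payer, with Medicaid providing another proxy for income". The SAP also says that it will consider machine learning to choose controls if that proves feasible, but it names no candidate variables and no method.

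Table 2, which is the same in both documents, has three utilization rows, all for the combined inpatient-or-ED outcome: "Hospital Visit (Inpatient or ED) 0-180 days 0.39 0.49 0.85 30% 397", "Hospital Visit (Inpatient or ED) 0-365 days 0.48 0.50 0.87 30% 278" and "Hospital Visit (Inpatient or ED) 90-365 days 0.40 0.49 0.92 30% 447".

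**The concern.** Comorbidity, payer and earlier health-care contacts are fixed before randomization and can be expected to predict hospital use. The team's own preliminary comparison (Protocol 6), whose outcomes included ED and inpatient admissions, matched on payer type. SAP section 4 itself justifies controls by the precision they bring. Leaving out predictors already in hand may keep avoidable residual variance in the treatment estimate.

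The margin is smaller for hospital use than for the clinical outcomes. Against 500 planned subjects, Table 2 leaves 500 − 447 = 53 spare (10.6%) for 90-365 days, 500 − 397 = 103 (20.6%) for 0-180 days and 500 − 278 = 222 (44.4%) for 0-365 days. For six-month HbA1c it leaves 500 − 55 = 445 (89%). At stake are somewhat wider intervals on secondary outcomes, not the validity of any estimate.

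**Working it through.** **Inputs.** Mean, SD, k = √(1−R²) and the 30% target come from Table 2. Alpha and power come from the SAP's HbA1c simulation, "with power=80% and alpha=0.05 and planned sample size of 500", because Table 2 states neither; a two-sided test is assumed. Enrolment is planned for "at least 500 subjects (half in treatment").

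**Reproducing Table 2.** Total N = 4 × (1.96 + 0.8416)² × (SD × k / (0.30 × mean))².

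- 90-365 days: 31.40 × (0.49 × 0.92 / 0.12)² = 443.1, or 444 after rounding up per arm; stated 447.
- 0-180 days: 31.40 × (0.49 × 0.85 / 0.117)² = 397.9, or 398; stated 397.
- 0-365 days: 31.40 × (0.50 × 0.87 / 0.144)² = 286.5, or 288; stated 278. Rounding of the printed inputs, with the SD tied to the mean, spans 277 to 295.

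For 90-365 days, 90% power would give 594 and a one-sided test 350, so 80% power two-sided is the reading that fits.

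**R² implied by the table.** 1 − 0.85² = 0.278 (0-180), 1 − 0.87² = 0.243 (0-365), 1 − 0.92² = 0.154 (90-365).

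**Power at 500 as planned.** Power = Φ(0.30 × mean / (SD × k × √(4/500)) − 1.96).

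- 90-365 days: 0.12 / 0.0403 − 1.96 = 1.016, so 84.5%.
- 0-180 days: 0.117 / 0.0373 − 1.96 = 1.18, so 88.1%.
- 0-365 days: 0.144 / 0.0389 − 1.96 = 1.74, so 95.9%.

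**With added covariates, 90-365 days.** k² = 0.8464 is lowered by the assumed gain in R²; no document supplies that gain.

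| Assumed R² gain | Required N | Power at 500 | Power at 450 | Detectable reduction at 500 | Fall in SE |
|---|---|---|---|---|---|
| 0 | 444 | 84.5% | 80.6% | 28.2% | – |
| 0.02 | 434 | 85.4% | 81.5% | 27.9% | 1.2% |
| 0.05 | 418 | 86.6% | 82.9% | 27.4% | 3.0% |
| 0.10 | 392 | 88.7% | 85.2% | 26.5% | 6.1% |

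Required N falls by 444 − 418 = 26 to 444 − 392 = 52 over the 0.05 to 0.10 range. For 0-180 days, the same two gains take required N from 398 to 372 and 344, and power at 500 from 88.1% to 90.2% and 92.3%.

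**Degrees of freedom.** The table above does not charge for the extra terms. With k₀ controls already in the model (assumed 20 to 43, given the age bins and entry months), p added terms break even at a gain of 0.8464 × p / (500 − 3 − k₀). For p = 10 this is 8.464/477 = 0.018 to 8.464/454 = 0.019. For p = 5 it is about 0.009. Ten weak covariates worth +0.02 together would therefore gain almost nothing, while a list of about five needs only about +0.01.

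**The case against.** The strongest reply is that nothing is broken. A parsimonious covariate set is a legitimate choice, utilization is secondary, and all three tabled rows exceed 80% power at 500 on the plan's own inputs. The thinnest row is a supplementary window in SAP 3.3, while the full 12-month row needs only 278. The exclusion criteria (Protocol 8.2.3) remove several severe conditions, which narrows the range of comorbidity. Visits outside the Geisinger system may be missed, which weakens prior counts as predictors. All of this stands, and it is why the point is put as an efficiency gain of unknown size.

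Three stronger readings are tempting.

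- A reader might infer that the hospital-visit models ignore either prior ED or prior inpatient use. All three Table 2 rows are the composite, and for a composite the lag most naturally counts both. Only the inpatient-only and ED-only outcomes lack the other hospital visit type; for the composite, the missing visit type is outpatient.
- A reader might infer that the SAP's control list explains only 28%, 24% and 15% of the variance. The SAP attributes the tabled R² to baseline characteristics that it does not list. Some of the covariates proposed here may already be included, in which case part of the gain is already counted.
- A reader might infer that these analyses are underpowered. On the plan's inputs they are not. Stopping below 500, which the two-year recruitment limit allows, or an effect smaller than 30% would lower power. Those are questions about the sample and the target, and covariate choice did not create them.

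The machine-learning sentence is a partial answer at most, because it commits to nothing.

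**Conclusion.** The omission is real, and its consequence is modest. The SAP's utilization models do not use baseline comorbidity, payer or other prior visit types although the trial extracts them, so some removable noise may remain where the sample-size margin is smallest. The intent-to-treat estimate is valid either way, and the planned size already meets the 30% target. If the added covariates are worth 0.05 to 0.10 in R², 90-365-day power rises by about 2 to 4 points. At 0.02 the gain is below one point before the cost in degrees of freedom, and it could be nil with about ten terms. These figures assume a two-sided 5% test, 500 analysed subjects, an undiluted 30% reduction, and a tabled R² that does not already contain the proposed covariates. The documents do not support calling this a bias, a power failure or a known loss of precision.

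**What to change.** In SAP section 4, for utilization and payment outcomes, prespecify a short addition to the controls before outcomes are seen:

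- a baseline comorbidity count;
- payer at enrolment;
- the outpatient visit count in the 12 months before enrolment;
- for the inpatient-only and ED-only outcomes, the prior 12-month count of the other hospital visit type.

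Beside Table 2, state which covariates produced its R².

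The cost is a few lines of SAP text and a few degrees of freedom. No new data, visits or subjects are needed. The list should stay short, because many weak terms would cancel the benefit.
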